Doses will be escalated in the standard 3 + 3 fashion, starting with 5 x 10^9 colony forming units (CFU) to a maximum dose level of 1 x 10^{10} CFU. Dose cohorts of 3 subjects each will be treated. In the absence of dose-limiting toxicity (DLT) as defined in Section 6.1 Dose Limiting Toxicity assessed during the first treatment cycle, the dose will be escalated to the next dose level for the next 3 subjects. If DLT is seen in 1 of 3 subjects, another 3 subjects will be treated at that same dose. If DLT is seen in 2 of 6 subjects, then that dose level will be considered maximum tolerated dose (MTD) and the previous dose level will be selected as the recommended Phase 2 dose (RP2D). The RP2D will be selected based on an observed DLT rate of < 33%.

Treatment cycles can be repeated at the RP2D (or less) for an individual subject until a discontinuation criterion is met. Discontinuation criteria include documented disease progression, intolerable side effects not resolved with dose reduction or change in premedications or the subject completes 1 cycle of treatment post observation of complete response (CR) per RECIST 1.1 and immune-related RECIST criteria (irCR).

Sponsor:	Name of Finished Product:	Type of Treatment:
Advaxis, Inc.	ADXS11-001	Lm-LLO Immunotherapy

Further assessment of the RP2D level may be explored in an expansion cohort in subjects with persistent, metastatic, or recurrent carcinoma of the cervix who have failed conventional therapy to evaluate the safety and clinical activity of ADXS11-001. Treatment will continue for each subject until a discontinuation criterion is met. The end of treatment will be defined as 1 year after the last subject's first treatment or until that subject has met a discontinuation criterion. All subjects will be followed for adverse events (AEs) and serious adverse events (SAEs) from the time written informed consent is signed through the completion of the *Lm* surveillance period.

Safety will be assessed by comparing treatment-related AEs, changes in physical examinations, vital sign measurements, laboratory abnormalities and *Lm* surveillance monitoring.

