Sponsor:	Name of Finished Product:	Type of Treatment:
Advaxis, Inc.	ADXS11-001	Lm-LLO Immunotherapy

- Subjects who have undergone a major surgery or who have a new artificial implant and/or medical device which meets eligibility criteria must have a minimum 6-week time period elapsed from the time of surgery to the initiation of study treatment.
- Subjects who are receiving or are expected to receive future treatment with PI3K or TNFα inhibitors.

Test Product, Dose, Mode of Administration:

ADXS11-001 is a live attenuated bioengineered strain of Listeria monocytogenes (Lm)-LLO.

Reference Therapy:

None

Study Duration:

Each subject will participate in the trial for up to 5 years from the time the subject signs informed consent through the final study contact. The study duration includes an active study treatment phase (~24 months) and a 3-year *Lm* surveillance monitoring period, which includes 6 months of oral antibiotic administration to commence upon completion of the active study treatment phase or upon study discontinuation.

Criteria for Evaluation:

Safety: Recorded AEs; physical examinations, including vital sign measurements; clinical laboratory evaluations; *Lm* surveillance blood cultures

Efficacy: Tumor response and progression free survival (PFS)

Immunologic effects: Collection and analysis of peripheral blood

Statistical Methods:

Descriptive statistics will be used to summarize and evaluate the outcomes.

Demographic and baseline subject characteristics will be summarized. AEs will be classified and summarized by type, incidence, severity, and causality. All AEs will be summarized by subject, dose level, and prior recurrence history (aggressive/non-aggressive). All subjects who received at least 1 dose of ADXS11-001 will be included in the safety analyses.

Disease response will be tabulated for all subjects who receive ADXS11-001. PFS is defined as the time from first dose of study treatment until objective tumor progression or death. Subjects who have not progressed or who are still alive at the time of evaluation will be censored for the analysis. Kaplan-Meier curves and descriptive statistics will be used to summarize PFS.

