7.3 Subject Study Participation

Each subject may participate in the study for up to 5 years from the time informed consent is signed through the final study contact. This includes a study treatment phase (~24 months), a 3-year post-ADXS11-001 treatment *Lm* surveillance period which includes a prophylactic oral antibiotic administration period (6 months) and *Lm* surveillance monitoring approximately every 3 months for 3 years. It is expected that a subject will participate in the study until the completion of the full 3-year *Lm* surveillance period. However, following the completion of the 6 month oral antibiotic treatment, a subject will be eligible to participate in other investigational clinical studies.

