- Baseline tumor imaging and assessments must be performed within 28 days prior to the first ADXS11-001 infusion in the first study cycle. Subsequent tumor imaging and assessments will be conducted at Week 12 (±1 week) for the duration of study participation. Apparent progression within the first 12 weeks, not accompanied by clinical deterioration, should be confirmed ≥4 weeks later.
- Immune monitoring/T-cell samples will be collected immediately prior to each ADXS11-001 infusion (Day 1 of Weeks 1, 4, 7, and 10) and between 11-14 days after every ADXS11-001 infusion in Cycle 1 only.
- Cytokine samples will be collected **in Cycle 1 only** at 3 time points immediately prior to each ADXS11-001 infusion and 2 hours and 4 hours post infusion (±15 minutes- Day 1 of Weeks 1, 4, 7, and 10).

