8.4 End of Therapy Evaluations

End of therapy is not a visit. It is a list of assessments that must be completed upon the decision to discontinue a subject from study treatment. These evaluations include: a physical examination, ECOG Performance Status, vital sign measurements, weight, hematology, coagulation, and chemistry profiles, urinalysis, and imaging studies, if indicated. AEs and changes to concomitant medications will also be assessed and documented

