11.8 Discontinuation of Study Subjects

11.8.1 Subject Study Discontinuation Criteria

Subjects may withdraw consent at any time for any reason or be discontinued from the trial at the discretion of the investigator, should any untoward effect occur. In addition, a subject may be withdrawn by the investigator or the sponsor if enrollment into the trial is inappropriate, the trial plan is violated, or for administrative and/or other safety reasons.

A subject may be discontinued from the trial for any of the following reasons:

- Screen Failure
- AE/SAE
- Lost to Follow-Up
- Disease Progression
- Death
- Withdrawal of Consent by Subject
- Investigator Decision/Study Non-Compliance by Subject
- Achieved Complete Remission
- Completed Study (at least 24 months of study treatment)
- Other (specify)

In all cases, the reason for and date of withdrawal must be recorded in the eCRF and in the subject's medical records. The subject must be followed up to establish whether the reason was an AE, and, if so, this must be reported.

When a subject discontinues/withdraws prior to study completion, all applicable activities scheduled for the final assessment (End of Therapy assessments) should be performed at the time of discontinuation. Any AEs that are present at the time of discontinuation/withdrawal should be followed in accordance with the safety requirements outlined in Section 13.2 Collection of Safety Information.

The Investigator must make every effort to contact subjects who discontinue the study prematurely or are lost to follow-up and to schedule the end of therapy assessments. Attempts to contact such subjects must be documented in the subject's records (e.g., times and dates of attempted telephone contact, receipt for sending a registered letter).

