14.5.5 Analysis of Efficacy

All subjects who complete at least one cycle of ADXS11-001 treatment will be included in the efficacy analyses. The following are efficacy parameters for the study:

- 1. Objective Response Rate (ORR)
- 2. Duration of tumor response
- 3. Stable Disease Rate (proportion of CR, PR, SD)
- 4. Duration of Stable Disease (SD)
- 5. Progression free survival (PFS)

Tumor response will be evaluated by RECIST 1.1 and irRECIST criteria. The ORR will be calculated as the proportion of subjects who achieved CR/irCR or PR/irPR. The duration of response is defined as the time interval from CR/irCR or PR/irPR to disease progression or death. If the subject's disease remains responsive by the time of discontinuation or completion of the study, the duration will be censored at that time point. The stable disease rate will be calculated as the proportion of subjects who achieved CR/irCR, PR/irPR or SD/irSD. The duration of SD is defined as the time interval from CR/irCR or PR/irPR or SD/irSD to disease progression or death. If the subject's disease remains stable by the time of discontinuation or completion of the study, the duration will be censored at that time point.

PFS is defined as the time interval from first infusion of study treatment to disease progression or death. If the subject's disease has not progressed by the time of discontinuation or completion of the study, the PFS will be censored at that time point.

Efficacy parameters will be descriptively summarized by dose cohorts as well as for all cohorts combined. Tumor response will be summarized according to response category. Response rate and stable disease rate will be summarized by frequency table. For durations of response and SD/irSD as well as PFS, the Kaplan-Meier method will be used to estimate the median times. Descriptive statistics and Kaplan-Meier curves will be presented.

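### PFS, duration of response and duration of SD are censored at a study-status date that the protocol uses inconsistently, not at the last tumor assessment; on one reading this counts up to about 3 years without a scheduled scan as progression-free

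*Combined protocol and SAP*

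**What the plan says.** **Censoring rule.** Section 14.5.5 measures PFS from first infusion to progression or death. If the disease "has not progressed by the time of discontinuation or completion of the study, the PFS will be censored at that time point". For duration of response, if the disease "remains responsive by the time of discontinuation or completion of the study, the duration will be censored at that time point"; duration of SD has a parallel sentence.

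**Synopsis rule.** After defining PFS as time from first dose to objective progression or death, the Synopsis adds: "Subjects who have not progressed or who are still alive at the time of evaluation will be censored for the analysis".

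**When a subject leaves the study.**
- Section 7.3 allows up to 5 years of participation: "It is expected that a subject will participate in the study until the completion of the full 3-year" *Lm* surveillance period.
- Section 11.8.1 lists, among reasons for discontinuation from the trial, "Completed Study (at least 24 months of study treatment"). The same list includes AE/SAE and complete remission.
- The Synopsis and sections 8.5 and 11.5.2 start surveillance at the end of treatment or at study discontinuation, so discontinuation precedes surveillance there.

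**Imaging.**
- Table 5 marks tumor imaging at Screening, Week 12 and End of Therapy. The Follow-Up column is empty for imaging.
- Sections 8.5 and 11.5.2 list blood tests and cultures for surveillance. Section 8.4 asks at end of therapy for "urinalysis, and imaging studies, if indicated".
- Table 5 footnote 20 says: "Subsequent tumor imaging and assessments will be conducted at Week 12 (±1 week) for the duration of study participation". Section 8.1 item 17 and section 8.3 set 12-weekly imaging and give no stop date.

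**The concern.** A censored subject should leave the Kaplan-Meier risk set when progression can no longer be seen, which is normally at the last evaluable tumor assessment. Section 14.5.5 uses an administrative date instead. If that date falls well after the last scan, the subject sits in the denominator while only death can count against her, and the later part of the curve is held up.

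Those exposed are subjects who stop without documented progression: for toxicity, after complete response plus one cycle, or after about 24 months of treatment. They include the complete responders, on whom duration of response depends.

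Safety reporting closes little of the gap. Section 13.2 says progression need not be reported as an AE, and section 13.7.1 brings it in only if it leads to hospitalization or death. Section 7.3 also lets subjects join other investigational studies after the 6-month antibiotic course, and 14.5.5 has no rule for new anticancer therapy.

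**Working it through.** **1. The plan's own timeline.** About 24 months of treatment plus 36 months of surveillance = 60 months = 5 years, as section 7.3 states. The 36 months hold 36/3 = 12 surveillance blood draws and no marked scan; a 12-week scan schedule would give 156/12 = 13.

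**2. The gap under each reading.**

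| Censoring date | Time since last scan |
|---|---|
| End of surveillance (section 7.3) | up to about 36 months, plus time from last scan to treatment stop |
| End of treatment (11.8.1; usage in 8.5 and 11.5.2) | at most about 12 + 1 = 13 weeks, or 13/4.345 = 3.0 months |

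Example: SD at Week 24, then treatment stopped for an AE. The first reading censors at Week 24 + 156 = 180, the second near Week 24.

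**3. A Kaplan-Meier example by hand (assumed data, n = 15).** Progression is seen on scans at 2.76 months (5 subjects), 5.52 months (2) and 8.28 months (1). Seven stop without progression at 6.5 months, with last scan at 5.52.
- Both anchors: S(2.76) = 10/15 = 0.667; S(5.52) = 0.667 × 8/10 = 0.533.
- Last-scan censoring: 1 subject at risk at 8.28, so S = 0 afterwards.
- End-of-surveillance censoring (6.5 + 36 = 42.5 months): 8 at risk at 8.28, so S = 0.533 × 7/8 = 0.467, and it stays there at 12 and 36 months.
- Observed progressions contribute 5 × 2.76 + 2 × 5.52 + 8.28 = 33.12 person-months. Adding 7 × 5.52 gives 72; adding 7 × 42.5 gives 331.
- The median is 8.3 months under both anchors; only the tail differs.

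**4. Simulation (200,000 subjects per scenario).** The documents as available give no event rates, so all of these are assumptions: exponential progression with median 4 or 6 months; median survival after progression 8 months; stopping without progression at 1% to 10% per month; a 24-month treatment cap; scans every 12 weeks on treatment only; deaths counted as events.

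Hand check of the reference value: the last scan before 12 months is at Week 48 = 48/4.345 = 11.05 months. The probability of no progression by then is 0.5^(11.05/4) = 0.147, or 0.5^(11.05/6) = 0.279.

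12-month PFS, with the Kaplan-Meier median:

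| Non-PD stopping per month | Median progression 4 months | Median progression 6 months |
|---|---|---|
| Last-scan censoring, any rate | about 14%; 5.5 months | about 28%; 8.3 months |
| Censoring at treatment stop, any rate | 14%–15%; unchanged | 28%; unchanged |
| End of surveillance, 1%–2% | 17%–20%; unchanged | 30%–33%; unchanged |
| End of surveillance, 5% | 26%; unchanged | 39%; unchanged |
| End of surveillance, 10% | about 34%; about 7.9 months | 46%; about 11.0 months |

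Before competing progression, 5% and 10% per month amount to 1 − 0.95^12 = 46% and 1 − 0.90^12 = 72% per year.

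A second set of assumptions (10%–40% assigned to stop early, median PFS 3 or 6 months, median survival after progression 9–18 months) gave 9%–15% against 8%, and 30%–36% against 28%, with no change in the median.

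**5. The Synopsis sentence.** Censoring anyone who is not progressed *or* is alive leaves as events only subjects who are both progressed *and* dead. That contradicts the preceding sentence, where either event counts. Its censoring date, the time of evaluation, is also undefined.

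**The case against.** The strongest reply is that no section defines study completion as the end of surveillance. Section 7.3 only states an expectation, while 11.8.1 ties completion to 24 months of treatment and lists AE and complete remission as reasons to discontinue. On that usage the Week 24 subject and the complete responder are both censored near treatment stop, where the simulation shows essentially no bias. This stands. A reader might infer that every complete responder gains three years of unobserved response; the documents do not support that as a flat statement.

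A reader might also infer that surveillance certainly has no scans. Footnote 20, section 8.1 item 17 and section 8.3 can each be read as continuing 12-weekly imaging, and deaths count as events throughout. The empty Table 5 column and these texts conflict; neither settles the matter.

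Nor should the Synopsis sentence "The end of treatment will be defined as 1 year after the last subject's first treatment" be taken as another definition of study completion. It concerns the end of treatment only.

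A reader might infer from the Synopsis censoring sentence that PFS will turn into something close to overall survival. The definition just before it, and section 14.5.5, make a drafting slip far more likely.

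Finally, section 14.5.5 plans Kaplan-Meier medians and curves and names no 12-month rate, and the larger effects need high stopping rates that the documents do not give. That stands too, although the curves will be presented and their tails are affected.

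What remains is that the censoring date can differ by about 3 years according to which section the programmer follows.

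**Conclusion.** The point holds as a defect of specification with a conditional bias. Section 14.5.5 anchors three endpoints to a status date instead of the last evaluable assessment, and the protocol supports two incompatible dates.

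On the section 7.3 reading with no follow-up imaging, 12-month PFS is overstated by about 2 to 5 percentage points at 1%–2% per month non-PD stopping and by nearly 20 points at 10%. The median moves only at 10%. On the treatment-stop reading the bias is negligible. These sizes rest wholly on the assumed rates in the simulation.

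The Synopsis error does not depend on either reading.

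The primary objective is safety; PFS is secondary and descriptive, with about 15 subjects planned at the recommended dose. No error rate, sample size or dose decision changes. It should be fixed before analysis, so that the date is not chosen once the data are known.

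**What to change.** 1. In section 14.5.5, censor PFS, duration of response and duration of SD at the last evaluable tumor assessment (Day 1 if there is none after baseline), and before any new anticancer therapy. Section 9.1.11 already limits immune-related best overall response to assessments before subsequent therapy, so this aligns the endpoints.
2. In the Synopsis, change the censoring condition to not progressed *and* still alive, with the same censoring date.
3. Reconcile Table 5 footnote 20, section 8.1 item 17 and section 8.3 with the empty imaging cell under Follow-Up.
4. Reconcile the uses of study completion and discontinuation in sections 7.3, 8.5, 11.5.2 and 11.8.1.

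The cost is wording in the protocol and analysis plan. Last-assessment censoring itself needs no extra subjects or visits. Reported PFS and duration of response may be less favourable than under end-of-surveillance censoring.

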14.6 Interim Analysis

No formal interim analysis is planned for the study. However, AEs and toxicity reports will be monitored

15 INVESTIGATOR OBLIGATIONS

15.1 Compliance with the Protocol and Protocol Revision

International Conference on Harmonisation (ICH) Guidance on Good Clinical Practice ([GCP] CPMP/ICH/135/95) and Advaxis require the Investigator to be aware of his/her obligations in the conduct of this study. These obligations are listed in the sections below.

When a situation occurs that requires a temporary departure from the protocol, the Investigator or other physician in attendance should contact the medical monitor as soon as possible in order to discuss the situation and agree on an appropriate course of action. The investigator will describe the departure from the protocol and the circumstances requiring it on the eCRF.

The Investigator may not modify this protocol. Amendments initiated by Advaxis or its agents will be confirmed in writing in the form of a protocol amendment. All such amendments must be approved by the IRB/IEC; however, amendments that reduce risks to the subjects may be implemented prior to obtaining IRB/IEC approval. No additional subjects can be enrolled until the amendment is approved by the IRB/IEC.

Documentation of approval signed by the chairperson or designee of the IRB/IEC must be sent to Advaxis. If the revision is an administrative letter, investigators must inform and obtain approval from their IRB/IEC.

15.2 Informed Consent

The Investigator must ensure that subjects are clearly and fully informed about the purpose, potential risks, and other critical issues regarding clinical trials in which they volunteer to participate.

15.2.1 Informed Consent Procedures

Preparation of the consent form is the responsibility of the investigator and must include all elements required by the ICH, GCP, and applicable regulatory requirements and must adhere to GCP. The consent form also must include a statement that Advaxis, its agents, and the regulatory authorities have direct access to subject records. Prior to beginning the study, the Investigator must have written IRB/IEC approval of the informed consent form and any other information to be provided to the subjects.

The Investigator must provide the subject or legally acceptable representative with a copy of the consent form and written information about the study in the language in which the subject is most proficient. The language must be nontechnical and easily understood. The investigator should allow time necessary for the subject or legally acceptable representative to inquire about the details of the study. Informed consent must be signed and personally dated by the subject or legally acceptable representative and by the person

who conducted the informed consent discussion. The subject or legally acceptable representative should receive a copy of the signed informed consent form and any other written information provided to study subjects prior to the subject's participation in the trial.

15.2.2 Update of Informed Consent

The informed consent and any other information provided to subjects or legally acceptable representative should be revised whenever important new information becomes available that is relevant to the subject's consent and should receive IRB/IEC approval prior to use. The Investigator, or a person designated by the investigator, should fully inform the subject or legally acceptable representative of all pertinent aspects of the study and of any new information relevant to the subject's willingness to continue participation in the study. This communication should be documented. During a subject's participation in the trial, any updates to the consent form and any updates to the written information will be provided to the patient.

If a protocol amendment substantially alters the study design or increases the potential risk to the subject: (1) the consent form must be revised and submitted to the IRB/IEC for review and approval, (2) the revised consent form must be used to obtain consent from subjects currently enrolled in the study, and (3) the new consent form must be used to obtain consent from new subjects prior to enrollment.

